5 STUDY POPULATION

A sufficient number (up to 150) of subjects with a diagnosis of fecal incontinence in the general population of Mayo Clinic will be screened and consented for eligibility to participate in the study and to facilitate the enrollment of 60 subjects into the treatment period of the study. Of these, up to [REDACTED] [REDACTED] of the subjects will be recruited for the [REDACTED] sub-study.

The specific inclusion and exclusion criteria for enrolling subjects in this study are presented below. Exceptions to these inclusion and exclusion criteria must be discussed in advance and approved by the Principal investigator and sponsor. Any exemptions to the study entry criteria will be documented in the source documents and on the appropriate page of the case report form.

5.1 INCLUSION CRITERIA

Male and female subjects aged 18 years and older at screening who meet the following inclusion criteria and none of the exclusion criteria will be eligible for enrollment:

- Able to provide signed (written) informed consent

- Diagnosis of fecal incontinence, with duration of symptoms six months or longer with a history of at least one fecal incontinence (FI) episode per week or at least four episodes per month
- Subject comprehends study meaning and is capable of carrying out study duties
- Patient is fluent in English as study questionnaires have been validated using English
- If female and of childbearing potential, patient has had a negative urine pregnancy test within 21 days of the first day of the baseline visit
- If applicable, Patient agrees to use acceptable birth control (surgical sterilization, abstinence, approved hormonal contraceptives such as birth control pills, barrier methods such as condom or diaphragm used with a spermicide, or an intrauterine device (IUD)). If not applicable, the reason why shall be documented on the screening log.
- Subject is at least 18 years of age at time of consent
- Patients has failed conservative medical therapy (i.e., the use of bulking agents, anti-diarrheal agents (e.g., loperamide) and biofeedback therapy as appropriate) for Fecal Incontinence

5.2 EXCLUSION CRITERIA

Subjects who meet the following criteria will be excluded from enrollment:

- Unable or unwilling to provide informed consent or to comply with study procedures
- History of anorectal pathology in the past 6 months (perianal abscess or fistula, fecal impaction, or clinically significant rectocele).
- History of inflammatory bowel disease with active proctosigmoiditis
- History of rectal surgery in past 6 months where the Investigator determines that the use of the study device may be associated with an increased risk of complications.
- History of acute or chronic illness or history of illness or any other reason which in the opinion of the Investigator, could pose a threat or harm to the subject or obscure interpretation of laboratory test results or interpretation of study data such as frequent angina, Class III or IV congestive heart failure, etc. The reason for exclusion of any enrolled subject shall be documented on the screening log.
- Patient has known clinically-significant immune deficiency state (e.g., HIV infection).
- Patient is taking drugs with a low therapeutic index, such as warfarin, digoxin, and anti-seizure medications
- If patient has clinically suspected upper or lower gastrointestinal (GI) obstruction, they must be excluded or have been evaluated per standard of care and obstruction ruled out before screening. Determination of obstruction shall be documented on the screening log.
- History of fecal impaction with overflow diarrhea in the past 6 months
- History of Ileo-anal pouch
- History of allergy to silicone or one of its components
- Patient is pregnant and/or nursing
- Any other reason, which in the opinion of the Investigator, would confound proper interpretation of the study
- Patient whom, after training from a healthcare provider, cannot insert or expel the device themselves or with assistance from a caregiver
- History of anal or rectal pain and/or rectal bleeding in the past month
- Subject cannot retain either device (10 or 13 mm) while ambulating at the screening visit

- Post baseline anoscopy examination, presence of an anal fissure, Grade III-IV internal hemorrhoids, or thrombosed external hemorrhoids.

In addition, subjects will not be eligible to participate in the Treatment Period if during the baseline period or at the [REDACTED] visit:

- Used rescue medications beyond those allowed by the protocol
- demonstrated lack of compliance (for e.g., did not complete bowel diaries for 3 days in any week during the baseline diary period)

Subjects will not be considered for the optional [REDACTED] sub-study if:

- they are not eligible to proceed to the treatment period
- they have contraindications for [REDACTED] e.g., subjects have [REDACTED]
[REDACTED], such as, [REDACTED]
[REDACTED]
- American Society of Anesthesiologist (ASA) score of 4 or higher

5.3 LIFESTYLE CONSIDERATIONS

Not-applicable.

5.4 SCREEN FAILURES

Subjects who are candidates for enrollment into the study will be evaluated for eligibility by the Investigator to ensure that the inclusion and exclusion criteria have been satisfied and that the subject is eligible for participation in this clinical study. Subjects who consent to participate in the study but (i) withdraw before participating in the baseline bowel diary because they can retain neither device size at the screening visit or no longer satisfy eligibility criteria (e.g., because they developed an inter-current illness) or (ii) do not have 4 or more episodes of FI during the 4-week baseline diary period will be considered screen failures.

Subjects will be informed that they have the right to withdraw from the study at any time for any reason, without prejudice to their medical care, penalty, or loss of benefits. The Investigator also has the right to withdraw subjects from the study for any of the following reasons:

- Adverse events which, in the judgment of the Investigator, justify treatment study withdrawal
- Non-adherence to study device use regimen or protocol requirements
- Non-compliance with instructions
- General or specific changes in the subject's condition unacceptable for further treatment in the judgment of the Investigator
- Subject requires use of an unacceptable concomitant medication
- Subject no longer meets the study inclusion or meets exclusion criteria
- Subject request

- Sponsor or FDA terminates study
- Administrative reasons

If a subject is withdrawn or discontinued from the study, the primary reason for withdrawal from the study is to be recorded in the source documents. If the subjects withdraws or is withdrawn prior to consent, the reason should be documented on the screening log. If the subject withdraws or is withdrawn after consent, the reason should be documented on the Case Report Forms (CRFs). All subjects withdrawn prior to completing the study should be encouraged to complete study safety assessments. All adverse events should be followed to resolution as described in Section 7.

Subjects who withdraw from the study prior to completion of [REDACTED] will be included in study intent to treat analysis and additional subjects will be enrolled into the [REDACTED] sub-study to achieve the goal of [REDACTED] subjects completing all study activities per protocol. In the event that an enrolled subject does not wish to participate in the [REDACTED] sub-study and this subject continues to meet all study inclusion/exclusion criteria, that subject may proceed to the Fitting and Treatment phases of this study.

5.5 STRATEGIES FOR RECRUITMENT AND RETENTION

All men and women aged 18 years and older will be eligible to participate regardless of ethnicity. The study may enroll up to 150 subjects until 60 subjects have been treated with the study device. Up to [REDACTED] subjects will be enrolled in the [REDACTED] sub-study. It is anticipated that that subjects will be recruited over 10-12 months from the outpatient clinic and patient databases at Mayo Clinic, Rochester and by public advertisement. Potential subjects may be approached by advertising, letter, phone, in person, or by e mail. All patient-facing materials will have sponsor and IRB approval prior to use. It is anticipated that the distribution of sex, race, and ethnicity will be consistent with the 2016 American Community Survey (ie, White (86.1%), African American (6.4%), Asian (7.1%), American Indian (0.8%), and other (1.6%).

6 STUDY INTERVENTION

6.1 STUDY INTERVENTION(S) ADMINISTRATION

6.1.1 STUDY INTERVENTION DESCRIPTION

Figure 3: Minnesota Medical Technologies Anal Insert Device.

This Minnesota Medical Technologies Anal Insert Device is a non-sterile soft, flexible, liquid-filled anal insert meant for single use only (Figure 3). The device is self-inserted into the anal canal where the liquid-filled bulb of the device is designed to rest against, conform to, and provide a seal at the anorectal junction to prevent fecal discharge from the rectum. The liquid-filled shaft of the device is designed to conform to and fill the anal canal allowing the pressure from the internal and external anal sphincters to seal the canal. The device's external retainer flare is designed to rest against the outside of the anus and prevent migration of

total number of pages includes protocol pages and table of contents

the insert into the anal canal and rectum. These mechanisms are designed to work together to prevent the involuntary leakage of fecal matter through the anal canal.

Subjects will be instructed to grasp the applicator and device retainer in their hand (**Figure 3**). After relaxing their anorectal muscles, subjects will gently insert the device until the retainer rests on the anus. The applicator is to be withdrawn and discarded. The bulbous tip is designed to facilitate retention of the device in the rectum.

6.1.2 DEVICE ADMINISTRATION

The sizes to be evaluated in this study are:

- Minnesota Medical Technologies Anal Insert Device 10 mm size – to be inserted in the anorectum during the day. Subjects who have nocturnal FI should also use the device at night.
- Minnesota Medical Technologies Anal Insert Device 13 mm size – to be inserted in the anorectum during the day. Subjects who have nocturnal FI should also use the device at night.

At the screening visit, the 10 mm, and, if necessary thereafter, the 13 mm device will be inserted into the rectum to determine if the device stays in situ while subjects are ambulating. Subjects who can retain neither device size will be withdrawn from the study.

Study subjects eligible for the study at the end of the baseline period will be given instructions as to ordering the study devices to be shipped to them by Minnesota Medical Technologies. The clinical site will train study subjects in the proper use of devices.

Eligible study subjects will proceed to a up to 4-week fitting period where subjects will evaluate which of two device sizes (10mm or 13mm) is preferred. Subjects who can retain the 10mm device at the screening visit will begin the fitting period with the 10mm device. Subjects who cannot retain the 10 mm but can retain the 13 mm device will begin the fitting period with the 13 mm device. The sequence of events for the fitting period will be as follows:

- 1) Subjects who begin with the 10 mm device will use the device for a minimum of 2 weeks during the fitting period. , Subjects will be asked to complete daily bowel diaries to determine the percent reduction in FI episodes, and subject comfort will be assessed using question #7 on the QUEST questionnaire. If greater than or equal to 75% reduction in FI episodes is observed during this fitting period, the subject will proceed immediately to the treatment period and will continue using the 10mm device for the entire treatment period. If the reduction in FI episodes is less than 75%, and the QUEST score is 1-2 (indicating dissatisfaction with comfort), the subject will proceed immediately to the treatment period and will continue using the 10mm device for the entire treatment period. If the reduction in FI episodes is less than 75%, and the QUEST score is 3-5 (indicating satisfaction with comfort), the participant will use 13 mm devices

for a minimum of 2 weeks as their fitting period and complete daily bowel diaries. At the end of this fitting period, the subject comfort will be reassessed with question #7 of the QUEST questionnaire. Subjects who report QUEST scores of 1-2 (indicating dissatisfaction with comfort) with the 13mm device will use the 10mm device for the entire treatment period. However, subjects who report QUEST scores of 3-5 (indicating satisfaction with comfort) at the end of the fitting period will proceed immediately to the treatment period and will continue using the size 13mm device for the entire treatment period.

- 2) Subjects who begin with the 13mm device will use the device for a minimum of two weeks during the fitting period. Thereafter, the subject will proceed to the treatment period and will continue using the 13mm device for the entire treatment period.

Subjects will be contacted at least twice per month during the fitting period. Attempts will be made to space these calls at an interval of 7 days. The devices which they are assigned to receive will be dispensed to study subjects by Minnesota Medical Technologies for use during the treatment period.

The devices will be packaged individually. Each subject will self-administer the devices. Subjects will be provided instructions for how to order the device and also an Instructions For Use, both of which will have Institutional Review Board (IRB) approval prior to use.

After the treatment period, all individuals who withdraw for reasons other than personal preference (i.e., for medical reasons) and a minimum of 50% of all patients shall undergo an evaluation by anoscopy following the treatment period to assess for device related trauma

6.2 PREPARATION/HANDLING/STORAGE/ACCOUNTABILITY

6.2.1 ACQUISITION AND ACCOUNTABILITY

██████████ will ship study devices to the study site using a trackable courier for use in the ██████████. Accountability for the study devices at the study site is the responsibility of the Investigator and their designated staff as well as the subjects. The study site personnel will instruct subjects to use study devices are used only in accordance with this protocol. The Investigator may choose to assign Mayo clinic device accountability responsibilities to an appropriate Mayo study team member. Accountability records will include dates, quantities, batch/serial numbers, expiration dates (if applicable), and subject numbers. The Sponsor or its designee will review devices accountability at the site on an ongoing basis during monitoring visits and at the end of the study when all unused devices are returned or disposed of, per sponsor instructions.

Device accountability records will be maintained by Minnesota Medical Technologies to document the batch/serial number, quantity, size, and date shipped to or from subjects. Devices will be provided to subjects using a trackable courier. Subjects will be responsible for keeping their study devices secure and for confirming with the study site that they (the subjects) have disposed of all unused and used

devices. The exception to this process will be if a subject experiences a device deficiency or malfunction. In this case, the subject will be asked to return the device to the study site or to Minnesota Medical Technologies for analysis, using trackable courier as the shipping method.

6.2.2 FORMULATION, APPEARANCE, PACKAGING, AND LABELING

Study subjects eligible for the study at the end of the baseline period will be dispensed the devices. Clinical sites will train study subjects (or a caregiver) in the proper use of devices.

The sizes to be evaluated in this study are:

- Minnesota Medical Technologies Anal Insert Device 10 mm size.
- Minnesota Medical Technologies Anal Insert Device 13 mm size.
 - o The devices will be packaged individually for patient use. Each subject will self-administer the devices

Study devices are packaged in kits for subjects enrolled in the study.

Study packages will contain the following information:

- Caution: Investigational device - Limited by United States Law to Investigational Use.

Study packages will not bear any statement that is false or misleading in any manner or represents that the study device is safe or effective for the purposes for which it is being investigated.

A copy of package labeling is provided under separate cover. Any changes to package labeling during the study, if applicable, will be provided under separate cover to the IRB and study site.

6.2.3 PRODUCT STORAGE AND STABILITY

All study devices are for investigational use only and are to be used only within the context of this study. All study devices will be supplied by Minnesota Medical Technologies.

The device is provided non-sterile in individual single-use packages which are shelf-stable at ambient temperature. Device size is indirectly indicated on the package label with a device code [REDACTED] [REDACTED]. Multiple individually packaged devices and a single IFU sheet are placed in a box for distribution to subjects. Study site must store devices in a secure location accessible only to authorized personnel.

6.2.4 PREPARATION

No special preparation is required for this device. The device will be removed from the package and inserted by the subject according to the instructions for use.

6.3 MEASURES TO MINIMIZE BIAS: RANDOMIZATION AND BLINDING

This is a within-subject control study with a 4-week baseline period followed by a 2 to 4-week fitting period and a 4-week treatment period. Up to [REDACTED] subjects who meet all inclusion and meet no exclusion criteria at the end of the baseline phase of the study may be included in the optional [REDACTED] sub-study

Subjects who are candidates for screening into the study will be evaluated for eligibility by the Investigator to ensure that the inclusion and exclusion criteria have been satisfied. Once the subject signs the informed consent, they are considered enrolled in the study. At that time, the study site personnel will register the subject and assign a sequential and unique subject number. Once a subject number has been assigned, it cannot be reused.

6.4 STUDY INTERVENTION COMPLIANCE

In order to evaluate the efficacy, safety and tolerability of the study device, it is critical that subjects use the study device as directed. All unused devices will be disposed of. Only one device is to be used at a time. All study devices are to be self-administered by the study subject or a trained caregiver. Subjects will be required to answer a question using the daily stool diary regarding administration of their study devices each day during the treatment period.

If a subject does not receive or use all assigned study devices, the reason is to be recorded in source documents and the CRF.

Subject will be contacted via telephone by the study site personnel during the study to encourage the subject to be compliant in completion of daily bowel diaries and questionnaires and to ensure reporting of adverse events.

6.5 CONCOMITANT THERAPY

Concomitant procedures: conducted during the study, including those used to treat adverse events, are to be reported in the source documents and on the CRF. Exceptions to inclusion and exclusion criteria must be discussed in advance and approved by the Principal investigator and sponsor. Any exemptions to the study entry criteria will be documented in the source documents and on the appropriate pages of the case report form, including protocol deviations.

Permitted Medication: Subjects must be on a stable dose of any chronic concomitant medications while participating in the study. This is defined as no changes in regimen for at least 2 weeks prior to

Day 1. [Daily adjustments of insulin doses or other medications used for non-gastrointestinal diseases (e.g., diuretics) are permitted.]

If it becomes necessary for a subject to take any other medication during the study, the specific medication(s) and indication(s) must be discussed with the Investigator prior to beginning this medication. All concomitant medications taken during the course of the study must be recorded in the source documents and the CRF.

Prohibited Medication and Substances: Medications that could impact the efficacy assessments during the study are prohibited. Subjects must withdraw from opioids at least 48 hours prior to the baseline period and throughout the study participation (except as protocol defined rescue medications). Other medications that alter gastrointestinal GI transit including [REDACTED]

[REDACTED] will be permitted as long as these medications are prescribed for regular (i.e., not as needed) use and the dose is stable for 2 weeks before the study. Drugs with a low therapeutic index, such as [REDACTED] medications are prohibited. All medications shall be reviewed and dis/approved by the investigator or sub-investigator on a case by case basis). Medications that may impact fecal incontinence will be tracked on a concomitant medication log.

6.5.1 RESCUE MEDICINE

Use of drugs after Day 1 which may impact efficacy evaluations is strongly discouraged. Subjects who need rescue medication, i.e., if they have 3 watery bowel movements in 24 hours, can use loperamide as needed at a dose of 2 mg every 6 hours, with no more than four doses over the course of 24 hours and no more than seven doses over the course of 48 hours. Subjects who need rescue medication for constipation, after three full days without a bowel movement, can receive 1-2 bisacodyl 5 mg tabs or a bisacodyl suppository (10 mg). In addition, subjects who need relief of mild pain can use analgesic drugs such as NSAIDs and COX-2 inhibitors for up to two doses per week. Intake of acetaminophen up to 1.5g per day in divided doses is permissible. Subjects who need rescue medication for constipation, after three full days without a bowel movement, can receive 1-2 bisacodyl 5 mg tabs or a bisacodyl suppository (10 mg).

6.6 DISCONTINUATION OF STUDY INTERVENTION

This study may be prematurely terminated if, in the opinion of the Investigator or Minnesota Medical Technologies or the Institutional Review Board, there is sufficient reasonable cause. Written notification documenting the reason for study termination will be provided to the Investigator or Minnesota Medical Technologies by the terminating party and all required regulatory notifications will be made.

Circumstances that may warrant termination include, but are not limited to:

- Determination of unexpected, significant, or unacceptable risk to subjects.

- Insufficient complete and/or evaluable data.
- Plans to modify, suspend or discontinue the development of the study device.

Should the study be closed prematurely, all study materials must be returned to Minnesota Medical Technologies or designee.

6.7 PARTICIPANT DISCONTINUATION/WITHDRAWAL FROM THE STUDY

If signs of a major side effect (e.g., rectal perforation) should occur, the subject will be treated as clinically indicated and Principal Investigator and Sponsor will be notified immediately. Such events will be reported on the case report form.

Patients with AEs will be evaluated by the investigator. An anoscopy will be performed to determine the etiology of anal pain or bleeding and if a significant anal-rectal abnormality is identified the patient will exit the study. Any data collected from a patient who is withdrawn because of an AE will be included in the ITT safety but not effectiveness summary. Any patient with a mucosal abnormality should be followed to resolution. After the treatment period, all individuals who withdraw for reasons other than personal preference (i.e., for medical reasons) and a minimum of 50% of all patients shall undergo an evaluation by anoscopy following the treatment period to assess for device related trauma.

Subjects will be informed that they have the right to withdraw from the study at any time for any reason, without prejudice to their medical care, penalty or loss of benefits. If the subject withdraws, they should be treated with standard of care. The Investigator also has the right to withdraw subjects from the study for any of the following reasons:

- Adverse events which, in the judgment of the Investigator, justify treatment study withdrawal
- Non-adherence to study device use regimen or protocol requirements
- Non-compliance with instructions
- General or specific changes in the subject's condition unacceptable for further treatment in the judgment of the Investigator
- Subject requires use of an unacceptable concomitant medication
- Subject no longer meets the protocol criteria (Section 4.2)
- Subject request
- Administrative reasons

If a subject is withdrawn or discontinued from the study, the primary reason for withdrawal from the study is to be recorded in the source documents and the Case Report Form. All subjects withdrawn prior to completing the study should be encouraged to complete study safety assessments.

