8 STATISTICAL CONSIDERATIONS

8.1 STATISTICAL HYPOTHESES

The hypotheses for the primary endpoints, which all apply to subjects with FI, are indicated below. For the primary study, these endpoints will be assessed for all 60 participants and separately for the 10 mm and 13 mm devices (versus baseline).

- 1. Primary Effectiveness Endpoint: A Relative Percentage Change in Episodes of Accidental Bowel Leakage (ABL) Determined by Comparing Treatment Results to Pre-treatment Results From the Baseline Period as Measured by Daily Diary Recordings . [Time Frame: Reduction in accidental bowel leakage from Baseline (Weeks 1-4) through Treatment period (approximately Weeks 9-12).]**

Measure Type	Primary
Measure Title	Primary Effectiveness Endpoint: A Relative Percentage Change in Episodes of Accidental Bowel Leakage (ABL) Determined by Comparing Treatment Results to Pre-treatment Results From the Baseline Period as Measured by Daily Diary Recordings.
Measure Description	This primary effectiveness endpoint will be calculated as a relative percentage of the baseline Accidental Bowel Leakage (ABL) using the following equation: % reduction in ABL = 100*(baseline period ABL - treatment period ABL) / (baseline period ABL)
Time Frame	Reduction in accidental bowel leakage from Baseline (Weeks 1-4) through Treatment period (approximately Weeks 9-12).

Secondary Efficacy Endpoint(s):

- The mean % reduction in Fecal Incontinence Severity Index (FISS) score from the baseline period to the end of the treatment period, calculated according to the following equation: % reduction in FISS = 100% (baseline period FISS - end treatment period FISS) / (baseline period FISS).
- The proportion of subjects in whom the frequency of FI episodes during the treatment period is greater than or equal to 75% lower than the frequency observed during baseline period.
- The proportion of subjects in whom, during treatment period, the device will reduce the number of days with FI by 50% as compared to baseline.
- The proportion of subjects in whom the device will reduce the volume of FI during the treatment period as compared to baseline.
- The proportion of subjects in whom the Minnesota Medical Technologies Anal Insert Device reduces the proportion of FI episodes which are associated with diarrhea.
- The proportion of subjects in whom the Minnesota Medical Technologies Anal Insert Device reduces the number of episodes of passive and of urge FI

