8.3 POPULATIONS FOR ANALYSES

Male and female, aged 18 and above, with a diagnosis of fecal incontinence. For the main and the sub-study, the analyses will follow the intent to treat (ITT) paradigm with all subjects randomized included in the analyses. Subjects with missing values for a particular endpoint will have their missing values imputed using the corresponding overall mean value from all subjects with non-missing data for that endpoint. An adjustment in the ANCOVA error degrees of freedom (subtracting one for each imputed value) will be made to account for the imputation. A similar adjustment for the Wilcoxon rank sum test (adjusting the degrees of freedom for the t-approximation) will also be examined. Similar analyses will be performed for the completer cohorts, i.e., all subjects who completed the 4 week treatment bowel diary and the [REDACTED] sub-study. For the bowel diary study, the modified ITT (mITT) cohort, which comprises those subjects who entered treatment and completed at least 1 week of device use will also be considered.

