8.4.2 ANALYSIS OF THE PRIMARY AND SECONDARY EFFICACY ENDPOINT(S)

[REDACTED]
detailed methods for the analyses outlined below,

All bowel diary parameters (e.g., stool frequency, form, urgency, use of rescue medications, and FI) will be averaged first for each day and then over 4 weeks (baseline period and the last 4 of 12 weeks (approximately Weeks 9-12, treatment period) in each subject. These responses will also be assessed using ANCOVA models, with the corresponding baseline value as the primary covariate. [During the fitting period (approximately weeks 5-8), bowel diaries and questionnaires will be maintained to determine the right size of device. However, these data will not be used to evaluate the efficacy of the device.]

The analyses of the primary and secondary quantitative endpoints will utilize analysis of covariance (ANCOVA) models using corresponding baseline measurements, if available, as covariates. The adequate relief endpoint will first be summed over 4 treatment weeks, and then assessed using the Wilcoxon rank sum test. Treatment effects between groups (i.e., 10 mm vs 13 mm) will be evaluated, as appropriate with ANCOVA adjusted for the baseline variable. Individual adverse events (AEs) will be summarized and, where appropriate, (i.e., for parameters that are recorded during baseline and treatment bowel diaries such as pain during defecation), the overall frequency of AEs be compared using the Wilcoxon rank sum test. For the volume of FI episodes, a weighted score will be computed as follows (proportion of minor episodes*2 + proportion of major episodes*3).²⁵ An FI episode is defined as any episode of stool leakage that is more than a stain. A “minor FI episode” is more than a stain but not an entire bowel movement. A “major FI episode” is an entire bowel movement.

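### Section 6.7 removes adverse-event withdrawals from the effectiveness summary, section 8.3 makes no such exception, and 8.3 defines the main-study ITT set by a randomization the main study does not have

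*Combined protocol and SAP*

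**What the plan says.** - Section 6.7, on subjects withdrawn because of an AE: "Any data collected from a patient who is withdrawn because of an AE will be included in the ITT safety but not effectiveness summary".
- Section 8.3, for the main study and the sub-study together: "the analyses will follow the intent to treat (ITT) paradigm with all subjects randomized included in the analyses".
- Section 8.3, on missing data: "Subjects with missing values for a particular endpoint will have their missing values imputed using the corresponding overall mean value", the mean being taken over subjects with data. One error degree of freedom is subtracted in the ANCOVA for each imputed value.
- Section 8.3 adds two further sets: completers of the 4-week treatment diary, and an mITT set of subjects who entered treatment and used the device for at least one week. Neither has an AE exception.
- Section 8.1, on the primary study: "these endpoints will be assessed for all 60 participants and separately for the 10 mm and 13 mm devices".
- Section 6.3, on the main design: "This is a within-subject control study with a 4-week baseline period followed by a 2 to 4-week fitting period", and then a 4-week treatment period. Device size follows from the screening retention test and the fitting period (4.1, 6.1.2). Subjects are randomized to a size only in the optional sub-study (7.1).
- Section 8.4.2, on diary variables: "will be averaged first for each day and then over 4 weeks". The visible text sets no minimum number of diary days. The opening of 8.4.2 is redacted.

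**The concern.** Section 6.7 selects the effectiveness set on something that happens after treatment starts and may be caused by the device. Poor tolerance is one way an insert can fail: section 2.2 describes earlier anal plugs as poorly tolerated. An AE here need not be device-related (7.3.1), so not every such exit is a device failure, but some will be.

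Two analysts, one following 6.7 and one following 8.3, could report different primary results from the same data, and the choice could be made after the data are seen. The study is open label with one treated group, so selective exclusion passes straight into the estimate. The objectives table in section 3 justifies the primary endpoint by substantial equivalence to a predicate, and section 2.1 describes the predicate result it cites (62% of subjects with at least a 50% reduction) as an intent-to-treat figure. A set without AE withdrawals would be a poor match for that comparison.

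**Working it through.** **1. The plan's own figure.** Section 8.2 claims 90% power at n=30 for an exact two-sided binomial test at 0.05, 30% against 60%. With at most 0.025 in each tail, the test rejects at 15 or more (upper tail 0.017 at 30%) or at 3 or fewer. Power is 0.903. The figure reproduces, so the point does not rest on a sample-size error.

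**2. One subject, each rule.** Take a subject who starts treatment, keeps the diary and leaves for an AE in treatment week 3.

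| Rule | In effectiveness? |
|---|---|
| 6.7 | No; no data used |
| 8.3 mITT | Yes; more than one week of use |
| 8.3 ITT | No AE exception, but membership depends on randomization |
| 8.3 completers | No; treatment diary not completed |
| 8.1 | Counted among the 60, if the phrase is read as a denominator |

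The conflict between 6.7 and mITT needs no inference about redacted text.

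**3. The ITT definition.** The sentence in 8.3 covers the main study, where nobody is randomized. Read literally, the main-study ITT set has no members.

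**4. Mean imputation.** Let n subjects have data with mean m, and let k have none. Imputing m gives (n·m + k·m)/(n + k) = m, the same unadjusted mean or proportion as dropping the k subjects. The degrees-of-freedom adjustment concerns precision and does not move the estimate.

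**5. Illustration for percent reduction.** The documents give no AE-withdrawal rate, so these inputs are assumptions: 60 treated (4.1), d AE withdrawals, a mean reduction of 50% in those retained, and a mean reduction of r in withdrawals.

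- Under 6.7: 50%, whatever d and r are.
- All treated: (50·(60 − d) + r·d)/60.

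| d | r | 6.7 | All treated |
|---|---|---|---|
| 6 | 0% | 50.0% | (50·54)/60 = 45.0% |
| 12 | 0% | 50.0% | (50·48)/60 = 40.0% |
| 6 | 25% | 50.0% | (2700 + 150)/60 = 47.5% |
| 12 | 25% | 50.0% | (2400 + 300)/60 = 45.0% |

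Section 8.3 falls between the two columns only to the extent that withdrawals have usable treatment diaries. If none has, it also gives 50%. If half have (a further assumption) and r=0, it gives 2700/57 = 47.4% for d=6 and 2400/54 = 44.4% for d=12.

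**6. Effect on the test verdict.** With equal tails, the 8.2 test at n=60 rejects upward at 26 or more. Count d withdrawals as failures and let the rest respond at 60%. Power is P(Bin(60 − d, 0.6) ≥ 26): 99.0%, 97.1%, 94.6% and 83.5% for d = 3, 6, 8 and 12. At the 70% response expected in 8.4.1 it is at least 99.3%.

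**The case against.** **6.7 may be a deliberate, specific exception to a general ITT paradigm.** That is possible, but 8.3 does not mention it, the mITT definition contradicts it, and the main-study ITT set would still be undefined.

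**6.7 and 8.3 may agree numerically.** The endpoint is defined over a 4-week period, and 8.3 does not say whether a partial diary is observed or missing. If partial diaries count as missing, both rules give 50% in the illustration. This stands: the gap between 6.7 and 8.3 cannot be sized from the documents. The all-treated column is likewise not a rule in the plan; it shows what exclusion can hide.

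**The redacted opening of 8.4.2 may hold diary rules.** This also stands, so the absence of a minimum-day or non-responder rule is a statement about visible text only. It does not make 6.7 and 8.3 agree.

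**Stronger readings that the documents do not support:**
- A reader might take 5.4, which says that certain withdrawals "will be included in study intent to treat analysis", as a further contradiction of 6.7. Its trigger is redacted, the same sentence goes on to replace sub-study subjects, and it does not mention effectiveness. It should not be relied on.
- A reader might take 8.1 as a direct rule for withdrawals. It mainly contrasts the pooled analysis with analysis by device size, so its support is indirect.
- A reader might infer serious inflation of the false-positive rate. At a true response of 30% and n=60, upward rejection rises from 2.0% to 5.8% with 6 excluded and 14.9% with 12, but only if every withdrawal is a non-responder. There is no inflation if they respond like the others. The calculation concerns the responder test rather than percent change, and depends on an exact-test convention that 8.2 does not state.

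**Conclusion.** The point holds, as a SHOULD-FIX. Sections 6.7 and 8.3 assign AE withdrawals differently, and the main-study ITT set has no workable definition. The bias favours the device if AE withdrawals do worse than others, which is plausible but not shown. Its size is unknown. In the illustration it is 5 or 10 percentage points for 6 or 12 withdrawals at 0% reduction, and 2.5 or 5 points if they reach 25%. The problem lies in the reported percent reduction and responder rates. A reader might infer that the trial's conclusion is at risk, but at the plan's target response rates the test verdict hardly depends on this.

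**What to change.** 1. In 6.7, state that subjects withdrawn for an AE stay in both the safety summary and the ITT effectiveness analysis, with their observed diary data.
2. In 8.3, define the main-study ITT set as all subjects who start the treatment period (the 60 of 4.1 and 8.1), and keep randomization as the criterion for the sub-study only. State how the ITT sentence in 5.4 relates to this set, because the sub-study precedes fitting and some subjects meant there may never start treatment. Report fitting-period exits by reason, with a sensitivity analysis that counts fitting-period AE exits as non-responders.
3. For responder endpoints, count treated subjects without sufficient treatment-period diary data as non-responders. Fix the minimum in advance and justify it against the baseline standard in 5.2, whose example of non-compliance is a subject who "did not complete bowel diaries for 3 days in any week during the baseline diary period".
4. For percent reduction, use observed treatment-period data as a rate per diary day. Do not impute the observed mean for withdrawals with no data. Report a sensitivity analysis with 0% reduction for those subjects alongside.
5. Keep mITT and completers as supportive analyses.

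The cost is a few sentences in 6.7 and 8.3, one diary-minimum rule and the sensitivity analyses. No new data are needed. The headline estimate may be somewhat lower, and counting non-response or 0% is conservative for subjects who leave for an unrelated AE.
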